#### 10.2 Ethics Review

The study protocol, site-specific informed consent forms (ICFs), participant education and recruitment materials, and other requested documents, including any subsequent modifications, will be reviewed and approved by the Independent Ethics Committee (IEC)/IRB.

#### 10.3 Informed Consent

The principles of informed consent in the ICH GCP guideline E6 (R2) will be implemented before any protocol-specified procedures or interventions are carried out. The consent form will describe the purpose of the study, the procedures to be followed, and the risks and benefits of participation. A copy of the consent form will be given to the participant, and this fact will be documented in the participant's record.

#### 10.4 Data Privacy

Participants' study information will not be released without their written permission, except as necessary for oversight by:

- The principal investigators or designees
- IRB/IEC
- Sponsor or designees, AND/OR
- Regulatory authorities

#### 10.5 Disclosure

Each study site will establish a standard operating procedure for confidentiality protection. Each site will ensure that study records including administrative documentation and regulatory documentation, as well as documentation related to each participant enrolled in the study, including ICFs, locator forms, CRFs, notations of all contacts with the participant, and all other source documents are stored in a secure manner.

#### 10.6 Biological Specimens and Data

All laboratory specimens, evaluation forms, reports, and other records that leave the site will be identified by coded number only to maintain participant confidentiality, unless otherwise required by local or state authorities, e.g., SARS-CoV-2 testing results, which are participant to local and state reporting that is name-based. Local public health agencies may contact participants diagnosed with SARS-CoV-2 for the purpose of surveillance and contact notification. Participants will be informed prior to SARS-CoV-2 testing that results are reportable and may lead to contact by local public health officials if results are positive for infection.

All records will be kept in a secure location. All computer entry and networking programs will be done with coded information. Clinical information will not be released without written permission of the participant, except as necessary for monitoring by the principal investigators

or designees, IRB/IEC, Office for Human Research Protections (or other local, US, and international regulatory entities as part of their duties), and/or the Sponsor or designees.

#### 11 OVERSIGHT

#### 11.1 Data Monitoring Committee

An independent DMC will be convened for this study consisting of at least 3 medical doctors, with expertise in infectious diseases, pulmonary/critical care, investigational drug development, and/or experienced in the management of hospitalized COVID-19 patients. The DMC will also include a biostatistician experienced in clinical trial design and analyses. The purpose of the DMC is to monitor the study for operational safety, and efficacy (including futility). The DMC will provide recommendations to the Sponsor as described in the DMC charter.

The DMC will conduct interim reviews when adequate data have been accrued. Open reports containing accrual and retention rates, participant characteristics, and SAEs will be sent to the DMC members prior to each scheduled or unscheduled DMC meeting. Only the DMC members (including the unblinded biostatistician) will receive password-protected closed reports containing unblinded study data. The DMC members will also have access to unblinded data at their request. Further details are contained in the DMC charter.

### 11.2 Quality Control and Assurance

#### 11.2.1 Monitoring

Study conduct will be monitored by site-independent monitors. Monitors will visit participating clinical research sites to review the individual participant records, including consent forms, eCRFs, supporting data, laboratory specimen records, and endpoints through laboratory and medical records (physicians' progress notes, nurses' notes, and individuals' hospital charts), to ensure protection of study participants, compliance with the protocol, and accuracy and completeness of records. The monitors also will inspect the sites' regulatory files to ensure that regulatory requirements are being followed and the sites' pharmacies to review product storage and management. When on-site visits to the participating clinical research sites are not feasible due to COVID-19 control measures and/or other institutional restrictions, remote monitoring visits will be performed per the study clinical monitoring plan.

#### 11.2.2 Protocol Deviations

Prospective approval of a protocol deviation of an enrollment criterion, also known as a protocol waiver or exemption, is not permitted.

Protocol deviations will be listed by treatment group for all randomized participants. Protocol deviations are defined as any variation from the protocol, including enrollment of a subject who did not meet all inclusion criteria or who met an exclusion criterion, or the failure to perform the assessments and procedures as specified in the protocol within the required time frames.

#### 11.2.3 Records

#### 11.2.3.1 Data Capture and Management

Participant information will be captured and managed by study sites on eCRFs by a web-based EDC tool.

#### 11.2.3.2 Records Retention

Investigator shall retain all study records until **at least 2 years** after the last approval of a marketing application in an ICH region and until there are no pending or contemplated marketing applications in an ICH region or **at least 2 years** have elapsed since the formal discontinuation of clinical development of the study drug. In the event that study records are relocated to a different location from the site location during this study retention period, the Investigator must notify the Sponsor and/or its designees.

#### 11.3 Study Completion/Termination

The Sponsor will register the study and post study results upon study completion or termination, regardless of outcome, on a publicly accessible website in accordance with the applicable laws and regulations.

The Sponsor also will notify, when required, the regulatory authorities and IECs/IRBs about the completion or termination of this study and send a copy of the study report synopsis in accordance with necessary timelines.

# 12 PUBLICATION POLICY

The Sponsor retains the rights to publish the results of this study. Details are included in the clinical trial agreement.

# 13 FUNDING

NeuroBo Pharmaceuticals, Inc. is the Sponsor of this study.

# 15 APPENDICES

# APPENDIX 1 WHO ORDINAL SCALE FOR CLINICAL IMPROVEMENT

Score	Status
1	Not hospitalized, no limitations on activities
2	Not hospitalized, limitation on activities and/or requiring home oxygen
3	Hospitalized, not requiring supplemental oxygen - no longer requires ongoing medical care
4	Hospitalized, not requiring supplemental oxygen - requiring ongoing medical care (COVID-19 related or otherwise)
5	Hospitalized, requiring supplemental oxygen
6	Hospitalized, on non-invasive ventilation or high flow oxygen devices
7	Hospitalized, on invasive mechanical ventilation or extracorporeal membrane oxygenation (ECMO)
8	Death

Reference: WHO R&D Blueprint: novel Coronavirus; COVID-19 Therapeutic Trial

Synopsis. Geneva, Switzerland. 18 Feb 2020

## APPENDIX 2 NATIONAL EARLY WARNING SCORE 2 (NEWS2)

The resulting observations are compared with a normal range to generate a single composite score, for instance based on the following diagram (an early modified NEWS):

Table 4 NEWS2

NEWS2 Score Select resp			Clinical risk		Response	
3 Respiration rate (per m	2	1	0	1 1	2	3
espiration rate (per n	initiate)	9-11	12-20		21-24	≥25
SpO₂ Scale 1 (%)						
≤91	92-93	94-95	≥96			
SpO₂ Scale 2 (%)						
≤83	84-85	86-87	88-92 ≥93 (air)	93-94 (O 2 )	95-96 (O 2 )	≥97 (O₂)
Air or O₂						
	02		Air			
Systolic blood pressure	e (mmHg)					
≤90	91-100	101- 110	111- 219			≥220
Pulse (per minute)						
≤40		41-50	51-90	91-110	111- 130	≥131
Consciousness						
			Alert			CVPU
Temperature (°C)						
≤35		35.1-36	36.1-38	38.1-39	≥39.1	

A summary of this scoring system can be accessed at https://www.rcplondon.ac.uk/projects/outputs/national-early-warning-score-news-2

For patients confirmed to have hypercapnic respiratory failure on blood gas analysis on either a prior or their current hospital admission and requiring supplemental oxygen should be noted. Scale 2 on the NEWS2 chart will be used to record and score the oxygen saturation for the NEWS.

The vital signs of the participant (including: pulse, respiratory rate, SpO2 (including room air or oxygen [with oxygen delivery and rate]), blood pressure (systolic and diastolic), and temperature will be entered into an eCRF. The individual parameters of the NEWS2 scoring system will be populated using these values.

Concurrently with determination of NEWS2, severity of participant's COVID-19 (Appendix 4) and subjective signs and symptoms of COVID-19 will be assessed and include presence or absence of: fever, cough (productive or non-productive), sore throat, malaise, headache, muscle pain, gastrointestinal symptoms (i.e., nausea, vomiting, or diarrhea), shortness of breath (with or without exertion), and respiratory distress.

This chart collected variable and scoring system is not intended to guide or modify standard-of-care at the respective investigative sites.

# APPENDIX 3 SEQUENTIAL ORGAN FAILURE ASSESSMENT (SOFA) SCORE

SOFA score	0	1	2	3	4
Respiration					
PaO 2 /FIO 2 (mmHg)	> 400	301-400	201-300	101-200	≤ 100
(kPa)	> 5.3)	(4.1-5.3)	(2.8-4.0)	(1.4-2.7)	≤ 1.3)
Coagulation Platelets (x10  /mm  )	> 150	101-150	51-100	21-50	≤ 20
Liver					
Bilirubin (mg/dl)	< 1.2	1.2-1.9	2.0-5.9	6.0-11.9	≥ 12.0
(µmol/l)	< 20)	(20-32)	(33-101)	(102-204)	≥ 204)
Cardiovascular					
Hypotension	No hypotension	MAP < 70 mmHg	Dopamine ≤ 5 or dobutamine (any dose)*	Dopamine > 5	Dopamine > 15
Central nervous system					
Glasgow coma score	15	13-14	10-12	6-9	< 6
Renal					
Creatinine (mg/dl)	< 1.2	1.2-1.9	2.0-3.4	3.5-4.9	> 5.0
(µmol/l)	< 110)	(110-170)	(171-299)	(300-440)	> 440)
or urine output				< 500 ml/day	< 200 ml/day

\* adrenergic agents administered for at least 1 h (doses given are in µg/kg/min)

Source: de Mendonça et al., 2000

FIO2=fraction of inspired oxygen; PaO2=partial pressure of oxygen.

# APPENDIX 4 CRITERIA FOR MODERATE, SEVERE, AND CRITICAL COVID-19

Severity	Criteria
Moderate	Development of one of the following:  1. Symptoms suggestive of moderate illness (fever, cough, sore throat, malaise, headache, muscle pain, gastrointestinal symptoms, AND shortness of breath with exertion, OR  2. Clinical signs indicative of moderate systemic illness with COVID-19, such as respiratory rate ≥20 breaths per minute, heart rate ≥90 beats per min, SpO 2 >93% on room air, AND  No criteria for Severe or Critical Severity
Severe	
 
Development of one of the following: 
 
Symptoms suggestive of severe illness, which could include any symptom of moderate illness PLUS shortness of breath at rest or respiratory distress, OR
 
Clinical signs indicative of severe systemic illness with COVID-19, such as respiratory rate ≥30 breaths per minute, heart rate ≥125 beats per min, SpO2 ≤93% on room air, AND
 
 
 
No criteria for Critical Severity
 

Critical	Evidence of critical illness, defined by at least 1 of the following:  1. Respiratory failure requiring at least 1 of the following:  a. Endotracheal intubation and mechanical ventilation, oxygen delivered by high flow nasal cannula (heated, humidified, oxygen delivered via reinforced nasal cannula at flow rates >20 L/min with fraction of delivered oxygen ≥0.5)  b. Noninvasive positive pressure ventilation (NIPPV), OR  c. Extracorporeal membrane oxygenation (ECMO) or clinical diagnosis of respiratory failure (i.e., clinical need for 1 of the preceding therapies, but preceding therapies not able to be administered in setting of resource limitation)
	
 
Shock (defined by systolic blood pressure (BP) <90 mm Hg, or diastolic BP <60 mm Hg or requiring vasopressors), OR
 
Multi-organ dysfunction/failure
 

Reference: FDA. COVID-19: Developing Drugs and Biological Products for Treatment or Prevention: Guidance for Industry. May 2020.

# **APPENDIX 5** LABORATORY ASSESSMENTS

Hematology (Local Laboratory Tests)*	Serum Chemistry (Local Laboratory Tests)*		
Hemoglobin	Blood urea nitrogen (BUN)		
Hematocrit	Creatinine		
Total WBC count with 5-part differential	Sodium		
Platelet count	Potassium		
	Chloride		
	Carbon dioxide		
	Glucose		
Coagulation (Local Laboratory Tests)*	Total bilirubin		
Partial thromboplastin time (aPTT)	Direct Bilirubin		
Prothrombin time (PT)	Alkaline phosphatase (ALP)		
International normalized ratio (INR)	Aspartate aminotransferase (AST)		
	Alanine aminotransferase (ALT)		
	Additional Tests (Central Laboratory Tests)		
	D-dimer		
	Cardiac troponin		
	Ferritin		
	LDH		
	CRP		
	Exploratory tests (e.g., IL-6, TF, MCP-1, IP-10)		

\* Denotes laboratory assessment used primarily to generate safety summaries

# **APPENDIX 6PK SAMPLE COLLECTION SCHEDULE (STUDY PART 1 ONLY)**

	Day 1, 2, 3, or Day 4					
SAMPLING SCHEDULE	Pre-Dose (i.e., within 30 minutes)	1 hour (+/- 30 minutes)	4 hour (+/- 30 minutes)	8 hour (+/- 30 minutes)	Pre-Dose to next study drug (i.e., within 30 minutes) administration	

Please refer to the Central Laboratory Manual for primary and back-up sample collection and processing instructions. Remaining blood plasma volume may be used for central laboratory and/or exploratory analyses (e.g., IL-6, tissue factor, MCP-1 and IP-10).

1. INTRODUCTION

The purpose of this document is to outline the planned statistical analyses at the end of Part 1 of data captured according to NeuroBo Pharmaceuticals protocol ANA001-001 titled "A Phase 2/3 Randomized and Placebo-Controlled Study of ANA001 in Moderate and Severe COVID-19 Patients" Version 4.0 (Amendment 3) dated 25 February 2021. This trial was registered on ClinicalTrials.gov Identifier NCT04603924 by ANA Therapeutics, which was acquired by NeuroBo Pharmaceuticals.

Tables, listings, and figures planned for the final analyses of Part 1 will be provided in a separate document.

2. STUDY OBJECTIVES

2.1 **Primary Objectives**

Part 1 of the study has one primary objective:

• Evaluate the safety and tolerability of ANA001 as therapy for moderate and severe COVID-19 patients

2.2 Secondary Objectives

The following is the secondary objective of Part 1 of the study:

- Evaluate the efficacy of ANA001 as therapy in moderate and severe COVID-19 patients
- Evaluate pharmacokinetics (PK) of ANA001

2.3 Exploratory Objectives

[figure not shown]
The exploratory objectives of Part 1 of the study:

- Evaluate clinical improvement using National Early Warning Score 2 (NEWS2)
- Evaluate the need and duration of rescue therapy
- Evaluate the effect on subjective symptoms of COVID-19
- Evaluate progression of COVID-19 from moderate or severe to more severe (i.e., moderate to severe, moderate to critical, or severe to critical)
- Evaluate the effect of ANA001 on requirement for oxygen and/or assisted ventilation
- Evaluate time to resolution of the WHO Ordinal Scale for Clinical Improvement
- Evaluate the effect of ANA001 on thromboembolic events
- Evaluate the relationship of ANA001 and markers of inflammation associated with acute respiratory distress syndrome (ARDS)

• Evaluate the relationship between ANA001 plasma concentrations and viral dynamics

3. STUDY DESIGN

This is a 2-part, multicenter, randomized, placebo-controlled clinical study of ANA001 in patients with moderate and severe COVID-19. The study duration for each participant will be approximately 62 days, including a 36-hour screening window. Screening and Day 1 may occur on the same day if screening criteria are met to confirm participant eligibility. After provision of informed consent, participants who satisfy all inclusion and no exclusion criteria will be randomized in a 1:1 ratio to be treated with ANA001 1000 mg BID or matching placebo. Randomization of participants will be stratified by oxygenation (SpO2 > 93 and < 98% on room air versus \leq 93% on room air), diarrhea (presence versus absence), and age (< 65 and \geq 65). Participants will be dosed within 36 hours of screening and as soon as possible following hospital presentation.

* An independent DMC will review Part 1 and Part 2 data on an ongoing basis until the study is complete.

Participants will receive capsules of ANA001 or matching placebo for 7 consecutive days (defined as 14 doses administered BID) according to the assignment made by the randomization and trial supply management (RTSM) system. Additionally, participants will receive continued standard of care therapy (per study site policies or guidelines). Dosing will continue until the treatment course is completed. If the participant requires mechanical ventilation or for any other reason is unable to swallow oral medication over the course of the study, ANA001 will be administered via nasogastric (NG) or orogastric (OG) tube in accordance with the appropriate section in the study Pharmacy Manual. If the participant is discharged prior to completing the

treatment course, the remaining study drug will be dispensed for at-home administration. Every effort will be made to complete the remaining study assessments for participants who are not able to complete the 7-day consecutive course of study drug.

Upon successful completion of Part 1, the safety and efficacy of ANA001 1,000 mg PO BID for 7 consecutive days will be evaluated in a larger population of patients in Part 2.

4. STUDY ENDPOINTS AND COVARIATES

The following endpoints will be considered for Part 1.

4.1 Demographic and Baseline Disease Characteristics

Demographics characteristics include:

- Age at baseline (including number of participants 18 40, 40 65, and ≥ 65 years)
- Sex at birth
- Ethnicity
- Race
- Height (m)
- Weight at Baseline (kg)
- Body mass index at Baseline (kg/m2) (including number of participants $> 30 \text{ kg/m}^2$).

Baseline disease characteristics include:

- WHO Ordinal Scale for Clinical Improvement score
- Number of days from first symptom to randomization
- Number of COVID-19 symptoms
- Number of co-existing conditions (0, 1, 2, 3, ≥4) as determined by medical history and other screening data, including
 - Age at screening >60 years
 - $\circ~$ Obesity, which is defined BMI at screening >30 kg/m^2 $\,$
 - Hypertension
 - Cardiovascular disease
 - Chronic lung disease
 - Chronic kidney disease
 - Chronic liver disease
 - Chronic immunosuppression, and
 - o Diabetes
- Respiration rate (<20, ≥ 20 to <25, ≥ 25 to <30, and ≥ 30 breaths per minutes)
- Pulse rate (<90, ≥ 90 to <100, ≥ 100 to <125, and ≥ 125 beats per minute)
- Temperature (\leq 38.3 versus > 38.3C)

- Peripheral capillary oxygen saturation (SpO₂) (>93% and <98% on room air versus <93% on room air)
- Fraction of Inspired Oxygen $(SpO_2/FiO_2) (\leq or > 200)$

4.2 Efficacy Endpoints

The primary endpoints for Part 1 of the study are safety endpoints including treatment-emergent adverse events (TEAEs), vital signs and laboratory (hematology, chemistry, and coagulation) parameters and are described in Section 4.3. The secondary and exploratory efficacy endpoints for Part 1 are described in the following sections.

4.2.1 Secondary Efficacy Endpoints

The secondary efficacy endpoint of Part 1 of this study is the median time (in hours) to hospital discharge (where discharge is defined as a score of 1 or 2 in the WHO Ordinal Scale for Clinical Improvement). For the purpose of deriving this efficacy endpoint, hospital discharge is defined as achieving WHO Ordinal Scale for Clinical Improvement score of:

- 1: Not hospitalized, no limitations on activities or
- 2: Not hospitalized, limitation on activities and/or requiring home oxygen.

4.2.2 Exploratory Efficacy Endpoints

The following are the exploratory efficacy endpoints of Part 1 of this study:

- Mean change from baseline in the NEWS-2 total score on Day 15
- Mean number of days on rescue treatment (COVID-19 therapies that are FDA approved or have emergency-use authorization) within 15 days after enrollment.
- Median time (in days) to resolution of subjective symptoms assessed by the Investigator to be potentially due to COVID-19 including: fever, cough (productive or non-productive), sore throat, malaise, headache, muscle pain, gastrointestinal symptoms (i.e., nausea, vomiting, or diarrhea), shortness of breath (with or without exertion), and respiratory distress
- Proportion of participants who's COVID-19 progresses to Severe or Critical within 15 days after enrollment
- Proportion of participants requiring ICU admission within 15 days after enrollment
- Mean change from baseline in SOFA score on Days 8 and 15
- Proportion of participants on Days 8 and 15 requiring:
 - Supplemental oxygen
 - High flow nasal cannula (HFNC) oxygen
 - Non-invasive positive pressure ventilation (NIPPV)
 - Mechanical ventilation
- Mean number of days on mechanical ventilation within 15 days after enrollment
- Mean number of oxygenation-free days within 15 days after enrollment

- Proportion of participants who achieve a score of 1 on the WHO Ordinal Scale for Clinical Improvement on Days 8 and 15
- Median time (in hours) to a 2-point improvement in the WHO Ordinal Scale for Clinical Improvement
- Incidence and severity of thromboembolic events within 15 days after enrollment
- Incidence of abnormal markers of inflammation to include CRP, IL-6, TF, MCP-1, and IP-10 on Day 8
- Mean change in viral load from baseline on Days 1, 4, 8, 15, and 28
- Median number of days to viral load undetectable by nasopharyngeal (NP) swab

4.3 Safety Endpoints

The following endpoints will be used to assess the safety and tolerability of ANA001:

- Incidence of treatment-emergent adverse events, serious adverse events, adverse events leading to study treatment discontinuation and adverse events leading to death
- Incidence of treatment-emergent potentially clinically significant laboratory abnormalities, including test results in the hematology, blood chemistry, and coagulation panels
- Incidence of vital signs abnormality, including temperature (°C), systolic and diastolic blood pressure (mmHg), pulse (beats/min), and respiratory rate (breaths/min).

4.4 Covariates

Sample size permitting, the following randomization factors will be considered as covariates:

- Oxygenation (SpO2 > 93 and < 98% on room air, \leq 93% on room air)
- Diarrhea (presence, absence), and
- Age at screening ($<65, \geq 65$).

Additionally, baseline score of the WHO Clinical Improvement Scale and the number of coexisting conditions will be used as covariates.

5. ANALYSIS POPULATIONS AND SUBGROUPS

5.1 Analysis Populations

The following populations will be considered for analysis:

Randomized Set: It includes all randomized participants who satisfied the inclusion and exclusion criteria described in this protocol.

Full Analysis (or Intent-to-Treat [ITT]) Set: It is the analysis population for the primary efficacy analysis. It includes all randomized participants classified according to the treatment arm into which they were randomized regardless of the actual treatment received.

Safety Analysis Set: It includes all randomized participants, classified according to the actual treatment received regardless of randomization assignment, who received any amount of study drug and have at least one post-baseline safety evaluation. This is the analysis population for all planned safety analyses.

5.2 Subgroups

Sample size permitting, the following subgroups will be considered:

- Age at baseline: $18 40, 40 <65, \ge 65$ years
- Sex: Male, Female
- Ethnicity: Hispanic or Latino, Not Hispanic or Latino
- Race: While, African American/Black, Asian, Other
- Symptoms duration: $< 7 \text{ days}, \ge 7 \text{ days}$
- Baseline score of the WHO Clinical Improvement Scale: 3, 4
- Co-existing conditions: chronic lung disease, cardiovascular or cerebrovascular disease, hypertension, diabetes, obesity, an immunocompromised state
- Peripheral Capillary Oxygen Saturation (SpO₂): > 93% and < 98% on room air versus \leq 93% on room air.

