### 5.3 Inclusion Criteria

To be included in this study, an individual must satisfy all the following criteria:

- 1. Willing and able to provide written informed consent (or their legally authorized representative) prior to performing study procedures. If necessary, emergency consent may be obtained per local procedures.
- 2. Hospitalized.
- 3. Understands and agrees to comply with planned study procedures, including ability and willingness to swallow multiple small capsules.
- 4. Male or female adult  $\geq$ 18 years of age at the time of informed consent.
- 5. Positive for SARS-CoV-2 by a standard RT-PCR assay or alternative Sponsor approved assay within 7 days of randomization and no more than 36 hours after hospitalization.
- 6. Presence of symptoms of lower respiratory tract infection (LRTI) including at least 1 of the following: fever, cough, sore throat, malaise, headache, muscle pain, or more significant lower respiratory tract symptoms, including shortness of breath (at rest or with exertion).
- 7. At least 1 of the following: respiratory rate (RR) ≥20 breaths per minute, room air SpO2 <98%, requirement for supplemental oxygen, heart rate (HR) ≥90 beats per minute, or temperature >38.3°C.
- 8. Access to a telemedicine platform for outpatient visits in cases where visits to the study site are not possible (e.g., telephone, smartphone, tablet, or computer).
- 9. Women of childbearing potential must agree to abstinence from heterosexual intercourse or use at least 1 form of contraception not including hormonal contraception from the day of screening through Day 30.

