### 5.4 Exclusion Criteria

If an individual meets any of the following criteria at screening, he or she is ineligible for this study:

1. Hospitalized, but no longer requires ongoing inpatient medical care (i.e. hospital discharge is anticipated in ≤24 hours.

- 2. Per the clinical judgment of the Investigator, the patient is not anticipated to survive >48 hours OR is under palliative care.
- 3. Evidence of critical illness, defined by at least 1 of the following:
  - Respiratory failure requiring at least 1 of the following:
    - a. Endotracheal intubation and mechanical ventilation, oxygen delivered by high flow nasal cannula (heated, humidified, oxygen delivered via reinforced nasal cannula at flow rates >20 L/min with fraction of delivered oxygen >0.5)
    - b. Noninvasive positive pressure ventilation (NIPVV), OR
    - c. Extracorporeal membrane oxygenation (ECMO) or clinical diagnosis of respiratory failure (i.e., clinical need for 1 of the preceding therapies, but preceding therapies not able to be administered in setting of resource limitation)
  - Shock (defined by systolic blood pressure (BP) <90 mm Hg, or diastolic BP <60 mm Hg or requiring vasopressors), OR
  - Multi-organ dysfunction/failure
- 4. Severe CNS conditions, e.g., acute stroke, severe confusion, or other acute mental status changes that may significantly determine duration of hospitalization and patient outcomes.
- 5. Chronic kidney disease requiring dialysis.
- 6. Anticipated transfer to another site, which is not a study site, within 72 hours.
- 7. Known allergy to the study drug or salicylate containing medications.
- 8. Suspected and/or confirmed pregnancy or breastfeeding.
- 9. Current or planned participation in any other interventional clinical trial under a US IND or EUA.
- 10. Patients receiving chemotherapeutic agents and/or immunomodulators (including glucocorticoids, monoclonal antibodies (Mabs), or plasma transfusions) for chronic disease conditions (e.g., malignancies, rheumatoid arthritis or other autoimmune diseases).

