7.4. Efficacy Analysis for Secondary Endpoint

The secondary efficacy endpoint for Part 1 of this study is the median time (in hours) from randomization to hospital discharge (where discharge is defined as a score of 1 or 2 in the WHO Ordinal Scale for Clinical Improvement).

Kaplan-Meier curves will be constructed to display time-to- hospital discharge. Participants who are lost to follow-up or ended study early prior to achieving clinical improvement will be censored at the day of the last obtained assessment of their WHO Ordinal Scale for Clinical Improvement. Participants who complete follow-up without hospital discharge will be censored at the day of their Day 60 visit. Participants who die for any reason during the study will be right-censored at Day 60 or date of death, whichever is earlier. For the analysis of this efficacy endpoint, missing scores of the WHO Ordinal Scale for Clinical Improvement will be assumed to be > 2 (*i.e.*, no hospital discharge). Median time-to-clinical improvement and corresponding 95% confidence interval will be estimated from the Kaplan-Meier curves and tabulated for each treatment group.

The Cox proportional hazard method will be used to calculate the hospital discharge rate ratio of ANA001 relative to placebo while controlling for the stratification factors, baseline WHO Ordinal Scale for Clinical Improvement, and number of co-existing conditions. Hospital discharge rate ratio is akin to a hazard ratio but for the beneficial outcome of hospital discharge.

A hospital discharge rate ratio > 1 indicates a benefit for ANA001. Treatment groups will be compared using a stratified log-rank test.

The above analyses will be produced for all participants in the Full Analysis Set and by baseline WHO Ordinal Scale for Clinical Improvement scores. Additionally, the same analysis will be produced for participants in the Per-Protocol Analysis Set and Safety Analysis Set.

If WHO Ordinal Scale are missing at baseline, 6 hours window after first dose will be added for baseline values.

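### SAP 5.2 sets the baseline WHO-score subgroups at 3 and 4, but the entry criteria lead to scores of 4, 5 and occasionally 6, so participants on oxygen fall in neither level

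*SAP*

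**What the plan says.** SAP 5.2 introduces its list with "Sample size permitting, the following subgroups will be considered" and gives one of the variables as "Baseline score of the WHO Clinical Improvement Scale: 3, 4". No other place in the SAP names levels for the baseline WHO score.

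Protocol Appendix 1 defines the relevant scores:
- Score 3 is worded as "Hospitalized, not requiring supplemental oxygen - no longer requires ongoing medical care".
- Score 4 is also a patient in hospital and off oxygen, but one who still needs care, whether for COVID-19 or for another reason.
- Score 5 is worded as "Hospitalized, requiring supplemental oxygen".
- Score 6 covers patients given non-invasive ventilation or a high-flow device.

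On entry, protocol 5.4 excludes at screening a patient who is "Hospitalized, but no longer requires ongoing inpatient medical care". Protocol 5.3, criterion 7, counts "requirement for supplemental oxygen" among the findings that qualify a patient.

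SAP 7.4 says that the time-to-discharge analyses will be "produced for all participants in the Full Analysis Set and by baseline WHO Ordinal Scale for Clinical Improvement scores". SAP 7.5.5 (ICU admission) and 7.5.8 (WHO scale) also tabulate by baseline score. None of these three sections says which scores.

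**The concern.** The two listed levels do not match the population that the protocol recruits. One describes patients who should not pass screening. The other holds only participants without oxygen. Participants on supplemental oxygen, whom the protocol expressly admits, have no level.

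A split of 3 against 4 therefore says nothing about oxygen need, which is the contrast that a baseline WHO-score subgroup would be expected to provide in a trial of moderate and severe disease. Because 5.2 is the only place that names levels, a programmer preparing the by-score tables for 7.4, 7.5.5 and 7.5.8 could carry 3 and 4 across and leave scores 5 and 6 out there too.

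Part 1 efficacy results have some weight. Under protocol 4.1 the DMC may recommend stopping for futility after Part 1. Under protocol 6.6.2 the sponsor may change the sample size or endpoints of Part 2 in the light of Part 1 efficacy data.

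**Working it through.** The plan states no figure to reproduce here. The check sets each Appendix 1 score against the entry criteria and then against SAP 5.2.

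| Score | State (Appendix 1, paraphrased) | Entry rule that applies | Expected at baseline | Level in SAP 5.2 |
|---|---|---|---|---|
| 1, 2 | Out of hospital | Inclusion 2 requires hospitalization | No | No |
| 3 | In hospital, off oxygen, care no longer needed | Exclusion 1, at screening | Nearly none | **Yes** |
| 4 | In hospital, off oxygen, care needed | Eligible | Yes | **Yes** |
| 5 | In hospital, on supplemental oxygen | Inclusion 7 admits | Yes | No |
| 6 | Non-invasive ventilation or high-flow device | Exclusion 3 bars NIPPV, and high flow above 20 L/min with delivered oxygen fraction above 0.5 | A few, on high flow below that threshold | No |
| 7 | Invasive ventilation or ECMO | Exclusion 3 | No | No |
| 8 | Death | Not applicable | No | No |

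The expected scores are 4, 5 and occasionally 6; the listed levels are 3 and 4. Only score 4 is in both.

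**Why nearly none at score 3, rather than none.** Exclusion 1 is applied at screening. SAP 6 takes baseline as the most recent value before dosing starts, and dosing may begin up to 36 hours after screening. If the baseline WHO score is missing, SAP 7.4 accepts a value up to 6 hours after the first dose. A participant who was eligible at screening could therefore have improved to 3 by baseline.

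**Does the SAP expect oxygen use at baseline?** Yes. SAP 7.2 gives rules for the baseline SOFA respiratory score at 1 and 2 L/min, and FiO2 values for nasal cannula at those flows. One section of the SAP plans for participants at score 5, while 5.2 has no level for them.

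**Is it the same scale?** SAP 4.2.1 words scores 1 and 2 as Appendix 1 does. The SAP does not define scores 3 to 8. It cites protocol Version 4.0; the protocol reviewed is Version 5.0. The list of appendices in Version 5.0 still labels Appendix 1 as the NIAID clinical status score, so the label has not been updated consistently. Identical numbering of 3 to 5 is therefore a reasonable inference, but it is not shown.

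**Size.** The documents give no share on oxygen at baseline. With N = 60 in Part 1 (protocol 9.1.1) and an assumed share p, the number in neither level is N × p:

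| Assumed p | In neither level |
|---|---|
| 30% | 60 × 0.30 = 18 |
| 50% | 60 × 0.50 = 30 |
| 70% | 60 × 0.70 = 42 |
| 90% | 60 × 0.90 = 54 |

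These are illustrations, not estimates.

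**The case against.** The strongest reply is that little depends on this line.

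- **The by-score outputs are not restricted.** SAP 7.4, 7.5.5 and 7.5.8 name no levels and do not refer to 5.2. Run on observed scores, they would show 5 and 6. This stands. What remains is that two sections can be read differently, which is a reason to align them.
- **Another severity subgroup exists.** The same list in 5.2 has room-air SpO2 above 93% and below 98% versus 93% or less. The 93% cut is among the signs that separate moderate from severe disease in protocol Appendix 4, and it is a randomization factor. So a reader might infer that the SAP has no way to look at effect by severity, but that would be wrong. The SpO2 variable is only a partial substitute, however. It needs a room-air reading, which protocol 6.1 asks for at screening only where clinically possible, and it classifies saturation rather than oxygen support.
- **Nobody is lost from the main analyses.** A reader might also infer that participants on oxygen are dropped from the efficacy analysis. They are not. They remain in the Full Analysis Set, and baseline WHO score is a covariate (SAP 4.4 and 7.4).
- **The stakes are limited.** The subgroups are conditional on sample size. This SAP covers Part 1 only, where the primary endpoint is safety. Protocol 9.3 plans no formal inference for Part 1, and SAP 9 makes no type I error adjustment. This stands in full.
- **Version 4.0 might have numbered the scale differently.** This cannot be excluded. If it did, the SAP would still have to be aligned with the current Appendix 1, because it does not itself say what 3 and 4 mean.

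None of these points makes 3 and 4 the right levels for the scale in the current protocol.

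**Conclusion.** The levels in SAP 5.2 are wrong as written when read against protocol Appendix 1 and the entry criteria. Level 3 should be nearly empty, level 4 holds only participants without oxygen, and participants on oxygen at baseline are in neither. The number affected cannot be taken from the documents; the 18 to 54 of 60 shown above rests wholly on the assumed shares.

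The effect is limited to this subgroup variable and to any output that borrows its levels. The Part 1 safety analysis, the overall time-to-discharge analysis and the Part 2 primary test are unaffected.

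One further inference should be resisted: that a baseline score of 3 is in itself an eligibility deviation. Exclusion 1 is judged at screening, and a participant who improved between screening and first dose has breached no entry criterion.

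The conclusion assumes that scores 3 to 5 carried the same meaning in protocol Version 4.0 as in the current Appendix 1.

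**What to change.** - In SAP 5.2, change the baseline WHO-score levels to 4 versus 5 or more, that is, not on oxygen versus on supplemental oxygen or higher support. Group any participant who has moved to score 3 by baseline with 4.
- In SAP 7.4, 7.5.5 and 7.5.8, state that the by-baseline-score outputs include scores 5 and above.
- Have the SAP reproduce or cite the current Appendix 1 scale, after checking the numbering of scores 3 to 5 against Version 4.0.
- Do not record a baseline score of 3 as an eligibility deviation unless exclusion 1 was met at screening.
- Carry the same levels into the Part 2 SAP.

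The cost is one line in 5.2, short clarifications elsewhere and revised table shells. No new data are needed. The change belongs before Part 1 is unblinded, which is when protocol section 9 requires the SAP to be final.
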